## VERSION HISTORY

SAP Version	Date	Primary Reasons for Amendment
1.0	03-MAR-2023	Not applicable
2.0	12-JUL-2023	To correct the derivation of the actual treatment for the 5mg/day group

## LIST OF ABBREVIATIONS

Abbreviation	Definition
AE	adverse event
ALT	aminotransferase
ANCOVA	analysis of covariance
AST	aspartate aminotransferase
BG	blood glucose
CI	confidence interval
CMO	comfort measures only
COVID-19	Coronavirus disease 2019
CRO	contract research organization
C ss	concentration at steady state
CYP	cytochrome P450
DC	decompressive craniectomy
DHA	Directions for Handling and Administration
DWI	diffusion-weighted imaging
ECG	electrocardiogram
eCRF	electronic case report form
ET	early termination
<hr/>	
GCP	Good Clinical Practice
GCS	Glasgow Coma Scale
GOS-E	Glasgow Outcome Scale – Extended
HPC	hemorrhagic progression of contusion
ICF	informed consent form
ICH	International Council for Harmonisation
ICL	imaging core laboratory
<hr/>	
IDMC	independent data monitoring committee
INR	international normalized ratio
IPH	intraparenchymal hematoma
IRT	interactive response technology
IV	intravenous
LAR	legally authorized representative
LHI	large hemispheric infarction
LKN	last known normal
<hr/>	
MRI	magnetic resonance imaging
mRS	modified Rankin Scale

NCCT	noncontrast computed tomography
NOAC	novel oral anticoagulants
NSx	neurosurgical intervention
OATP	organic anion transporting polypeptide
POC	point-of-care
PTT	partial thromboplastin time
PVC	polymerizing vinyl chloride
QTc	QT interval corrected for heart rate
rTPA	recombinant tissue plasminogen activator
SAE	serious adverse event
SAP	Statistical Analysis Plan
SD	standard deviation
SOC	standard of care
SUR1-TRPM4	sulfonylurea receptor 1-transient receptor potential melastatin 4 channel
SUSAR	suspected unexpected serious adverse reaction
TBI	traumatic brain injury
ULN	upper limit of normal

## 1. Introduction

This statistical analysis plan (SAP) provides details of all pre-planned statistical analyses for Study 252BN201 (protocol version 3.0). Any deviation to this SAP will be described in the Clinical Study Report (CSR).

## 2. Study Overview

### 2.1. Study Objectives and Endpoints

Primary Objective	Primary Endpoint
To determine if BIIB093 reduces brain contusion expansion by Hour 96 when compared to placebo. Measurements of contusion expansion are based on a comparison of the baseline images and the scans collected prior to and including 96-hour scan, or the scan obtained prior to DC, intraparenchymal hematoma (IPH) evacuation, or comfort measures only (CMO), if earlier.	Change in total contusion volume (hematoma plus perihematomal edema) as measured by brain imaging from baseline to 96 hours or prior to DC, IPH evacuation, or CMO if these procedures occur before 96 hours per the central review.
Secondary Objectives	Secondary Endpoints
To evaluate the effects of BIIB093 on acute neurologic status, functional outcomes, and treatment requirements.	

• Glasgow Outcome Scale – Extended (GOS-E) at Day 180

• Modified Rankin Scale at Day 90

• Proportion of participants requiring delayed intubation

 
Note: delayed intubation is defined as participants requiring intubation (for neurologic deterioration only) at any time between 24 hours and 96 hours postinjury.

To further differentiate the mechanism of action of BIIB093 compared to placebo on contusion expansion by examining differential effects on hematoma and edema expansion.	

• Change in total contusion volume (hematoma plus perihematomal edema) as measured by brain imaging from baseline to 24 hours or prior to DC, IPH evacuation, or CMO if these

## 2.2. Study Design

The Study 252BN201 is a multicenter, double-blind, multidose, placebo-controlled, randomized, parallel-group, Phase 2 study to evaluate the efficacy and safety of BIIB093 (intravenous glibenclamide) in participants aged 18 to 85 years old (inclusive) who have a clinical diagnosis of brain contusion with lesions within the supratentorial brain parenchyma totaling  $> 3$  mL at screening per investigator assessment of non-contrast computed tomography (NCCT) or site local radiologic assessment. Participants must have a score of 5 to 15 on the Glasgow Coma Scale (GCS) and have been functionally independent, in the opinion of the investigator, prior to index head injury. Details of the study design and inclusion/exclusion criteria are described in Section 7 and 8 of the protocol, respectively; see Figure 1 for a schematic of the study design.

[figure not shown]
The total duration of study participation for each participant will be approximately 180 days; this consists of a concurrent screening and enrollment period, a treatment period of 96 hours, and a follow-up period up to Day 180.

The primary endpoint for the study is at Hour 96. All randomized participants will be followed for 180 days unless consent is withdrawn.

The end of study for a participant is considered the final study assessment at Day 180 or the Early Termination (ET) Visit.

The end of the study is when the last participant completes the Day 180 Follow-up Visit or ET Visit

Figure 1: Study Design

h = hours; MRI = magnetic resonance imaging; NCCT = noncontrast computed tomography; SOC = standard of care; TT/LKN = time of trauma/last known normal.

Dosing must be started within 10 hours from time of trauma/last known normal and within 6 hours of hospital arrival. Dosing should be initiated within 1 hour of randomization and continue for 96 hours (4 days).

### 2.3. Sample Size Considerations

The study is planned to randomize approximately 160 participants. The primary endpoint for the study is the change in total contusion volume (hematoma plus perihematomal edema) as measured by brain imaging from baseline to 96 hours, or prior to DC, IPH evacuation, or CMO, if these procedures occur before 96 hours. Assuming the common standard deviation of 29 mL in contusion volume change from baseline, a sample size of 160 participants (40 each in the 3 mg/day dose or matching placebo arms and 40 each in the 5 mg/day dose or matching placebo arms) will have approximately 90% power to detect assumed average difference of 15 mL between the pooled active treatment groups (n=80) and pooled placebo groups (n=80) using 2 group t-test at a 2-sided significance level of 5%.

### 3. Definitions

#### 3.1. Dates and Points of Reference

The first date of starting study drug infusion (BIIB093 3 mg/day, 5 mg/day or the matching placebo) is referred to as study Day 1. For all the dates in the study

- If a date is on or after study Day 1  
Study Day = (date of interest) – (study Day 1) + 1
- If a date is before study Day 1  
Study Day = (date of interest) – (study Day 1)

Study Hour 0 is defined as the start time of the study drug infusion. For all the times in the study before and during the study drug infusion

- Study Hour = (hour of interest) – (study Hour 0)

For efficacy data that are summarized or analyzed by visit, data collected on all scheduled visits and all unscheduled visits will be mapped to an appropriate analysis visit using the windowing scheme shown in [Table 1](#). If there are 2 or more assessments available in the same analysis window for a subject, unless otherwise specified, the assessment that is closest to the target visit day/time will be used for analysis. If there are 2 or more assessments in the same analysis window with the same distance from the target visit day, the later assessment will be used.

**Table 1. Visit Windows for Efficacy Endpoints**

Volume Data		
Analysis visit	Target timepoint in hr	Analysis visit window
Screening	0	Most recent non-missing pre-dose value
Hour 24	24	[10, 38]
Hour 96	96	[76, 116]
GOS-E		
Analysis visit	Target visit day	Analysis visit window
Hospital discharge	7	(0, 23)
Day 30	30	[23, 60]
Day 90	90	(60, 135)

Day 180	180	$\geq 135$
mRS, [REDACTED] [REDACTED]		
Analysis visit	Target visit day	Analysis visit window
Day 90	90	(45, 135)
Day 180	180	$\geq 135$
GCS		
Analysis visit	Target timepoint in hour	Analysis visit window
Screening	0	Most recent non-missing pre-dose value
Hour 24	24	(12, 36]
Hour 48	48	(36, 60]
Hour 96	96	(84, 120]

Study visits and associated visit windows for all remaining analyses are specified in [Table 2](#), which are subject to change prior to the Day 4 administrative database lock. Study period in the table is defined in [Section 3.3](#). Detailed protocol-specified schedule of activities and study visits in Table 2 of the protocol are attached in [Appendix 1](#).

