5. SCHEDE OF ACTIVITIES

CONFIDENTIAL

The information contained herein may not be used, disclosed, or published without the written consent of
Biogen MA Inc.

Table 2: Schedule of Activities

	Screening/ Enrollment	Hours 0-12 ¹	Hour 24 (±6 h)	Hour 48 (±12 h)	Hour 72 (±12 h)	Hour 96 (±12 h) ²	Day 7 (±24 h) ³	Hospital Discharge (±24 h) ⁴	Day 30 (±7 d) ⁴	Day 90 (±14 d) ⁴	Day 180 (±14 d) ⁴	NSx/Comfort Measures (if applicable)	ET Visit
Inclusion/ exclusion criteria	X												
Informed consent	X												
Demographics, medical history, physical examination (including weight and height)	X												
TT/LKN	X												
NCCT ⁵	X ⁶		X			X ⁷						X	
GCS	X		X	X		X							
Pregnancy test (urine or serum)	X												
Blood alcohol level	X												
Blood sampling for coagulation panel (INR, PTT, fibrinogen)	X												
Blood sampling for hematology and blood chemistry	X							X					X ⁸
Blood sampling for LFTs	X		X	X	X	X	X						
Vital signs ⁹	X	X	X	X	X	X	X						X
Other assessments (ECG, [REDACTED])	(see Table 3 for ECG, [REDACTED] schedule of activities)												
Blood sampling for pharmacogenetics (optional) ¹⁰						X							
Enrollment/randomization (TT/LKN < 10 h)	X												

CONFIDENTIAL

The information contained herein may not be used, disclosed, or published without the written consent of Biogen MA Inc.

	Screening/ Enrollment	Hours 0-12 ¹	Hour 24 (±6 h)	Hour 48 (±12 h)	Hour 72 (±12 h)	Hour 96 (±12 h) ²	Day 7 (±24 h) ³	Hospital Discharge (±24 h) ⁴	Day 30 (±7 d) ⁴	Day 90 (±14 d) ⁴	Day 180 (±14 d) ⁴	NSx/Comfort Measures (if applicable)	ET Visit
Study treatment (TT/LKN < 10 h)			← 96-hour infusion → (see Section 4.5.1 for further details)										
Delayed intubation eCRF ¹¹			X	X	X	X							
BG measurement ¹²	X	X	X	X	X	X	X						
Concomitant therapy	X	X	X	X	X	X	X	X	X	X	X	X	X
Concomitant procedures ¹³	X	X	X	X	X	X	X	X	X	X	X	X	X
Craniectomy/comfort care/ cranioplasty assessment form(s)												X	
MRI ^{14, 5}						X ¹⁵						X	X ¹⁶
GOS-E								X	X	X	X		X
mRS										X	X		X
Review safety data and record AEs/SAEs ¹⁷	X	X	X	X	X	X	X	X	X	X	X		X
Brief suicide ideation/behavior assessment ¹⁸	X								X	X	X		X

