## 4. List of Planned Study Analyses

### 4.1. Interim Analysis

An interim analysis will be performed by an internal, independent, unblinded team when approximately 90 subjects are dosed and completed Hour 96 visit or terminated early, for administration purposes. The interim analysis will include all subjects who are in the mITT or safety population as described in the SAP. The interim analysis will include the following analyses:

- Demographic and baseline
- Exposure

- Efficacy – to include:
  - Change in total contusion volume at hours 24 and 96
  - GOS-E at hospital discharge, Day 30, Day 90 and Day 180
  - Change in hematoma volume at hours 24
  - Change in edema volume at hours 96
  - Change in total contusion volume by GOS-E by visit
- Safety – to include:
  - AEs/SAEs
  - Hypoglycemia
  - Laboratory
  - ECG

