#### 5.1.4. Missing Values for GOS-E

GOS-E at [REDACTED] 180 will be analyzed as a 7-category ordinal scale (1/2, 3, 4, 5, 6, 7, 8). Multiple imputation will be used to account for missing values for GOS-E. Death and vegetative state are scored as 1 and 2 in GOS-E and therefore no missing GOS-E values are expected due to death or vegetative state. Missing GOS-E values due to reasons other than death or vegetative state will be imputed based on a linear model performed on the GOS-E scores leveraging the information of the patient at other time points as well as the time patterns of all other participants. The model will include treatment as a classification variable and other covariates: GOS-E score at the previous timepoint, region (North America and RoW), age ( $\leq 70$ ,  $> 70$  years), baseline GCS (5-8, 9-12, 13-15), baseline contusion volume per investigator ( $> 3$  to 10 mL vs  $> 10$  mL). Imputed values will be rounded to the closest valid GOS-E score, 100 imputations will be conducted with random seed pre-specified, and each imputation will result in a complete dataset for all mITT participants.

The missing data pattern will be evaluated including reasons for missingness, missing data by randomized treatment group and visit, and potential covariates associated with missingness. Sensitivity analyses will be planned to evaluate the robustness of the results from the main analysis of GOS-E.

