### 5.6.3. Secondary Efficacy Endpoints

#### GOS-E at Day 180

GOS-E will be assessed as a 7-category ordinal scale (1/2, 3, 4, 5, 6, 7, 8) at discharge, Day 30, Day 90, and Day 180.

- GOS-E at Day 180 will be analyzed by randomized treatment based on observed data for the full analysis set using ordinal logistic regression adjusting for covariates specified in Section [5.6.1](#).

- Dichotomized GOS-E (0-4 versus 5-8) at Day 180 will be analyzed using binary logistic regression adjusting for covariates specified in Section [5.6.1](#).
- Multiple imputation for missing GOS-E values at Day 180 will be conducted as specified in Section [5.1](#). The analysis results from imputed datasets will be combined for inference using Rubin's rule.
- Descriptive statistics for GOS-E scores will be summarized by visit (see Section [5.1](#)).

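### SAP Table 1 assigns hospital-discharge GOS-E by a Day 1 to 22 date window, so scores from discharges on Day 23 or later cannot appear under discharge and are mapped to later visits

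*SAP*

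**What the plan says.** For efficacy data handled by visit, SAP section 3.1 refers to Table 1 and says that "data collected on all scheduled visits and all unscheduled visits will be mapped to an appropriate analysis visit using the windowing scheme shown in" that table. Where a window holds two or more assessments, "the assessment that is closest to the target visit day/time will be used for analysis"; at equal distance the later one is taken. The allowance for exceptions in that section attaches to this choice between records, and no exception for discharge appears elsewhere in the SAP.

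The GOS-E rows of SAP Table 1 are:

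| Analysis visit | Target day | Window | Study days covered |
|---|---|---|---|
| "Hospital discharge" | 7 | (0, 23) | 1 to 22 |
| Day 30 | 30 | [23, 60] | 23 to 60 |
| Day 90 | 90 | (60, 135) | 61 to 134 |
| Day 180 | 180 | ≥ 135 | 135 onward |

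Protocol section 5, Table 2, gives hospital discharge its own column, with a tolerance of 24 hours either side of the event, separate from Day 7 and Day 30. GOS-E is marked at discharge, Day 30, Day 90, Day 180 and early termination (ET), but not at Day 7. Protocol section 10.1 also asks for a GOS-E, where possible, when a participant is moved to comfort care.

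SAP section 5.6.3 says "GOS-E will be assessed as a 7-category ordinal scale (1/2, 3, 4, 5, 6, 7, 8) at discharge, Day 30, Day 90, and Day 180", and that "Descriptive statistics for GOS-E scores will be summarized by visit". SAP section 4.1 lists "GOS-E at hospital discharge, Day 30, Day 90 and Day 180" among the interim efficacy outputs, together with contusion volume change by GOS-E at each visit. SAP section 5.1.4 uses "GOS-E score at the previous timepoint" as a covariate when missing GOS-E is imputed.

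**The concern.** The schedule and the text of the SAP treat discharge as an event. Table 1 treats it as a fixed early timepoint. When the two disagree, the date rule decides, and the row no longer holds what its name says.

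Three things follow. Inclusion in the discharge row depends on length of stay, which is a post-randomization outcome; if treatment changes length of stay, the two groups are selected differently. A late discharge score does not simply disappear: it enters another visit's window and can push out the assessment scheduled there. And because the row is filled by date, scores that have nothing to do with discharge can be reported as discharge scores.

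At stake are the descriptive GOS-E tables, the discharge GOS-E seen by the unblinded team at the interim analysis, and possibly a covariate in the GOS-E imputation.

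**Working it through.** The plan states no figure for discharge GOS-E, so there is none to reproduce. Its sample size statement concerns the primary endpoint and does not depend on this point.

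**Step 1: where a discharge score lands.** Applying the windows above to the day of discharge:

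- Days 1 to 22: discharge row.
- Days 23 to 60: Day 30 row. Day 23 is excluded from the discharge window and included in this one.
- Days 61 to 134: Day 90 row.
- Day 135 onward: Day 180 row.

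So no score from a discharge on Day 23 or later can reach the discharge row.

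**Step 2: what happens in the Day 30 window.** The distance is |assessment day − 30|; the smaller distance is kept and a tie goes to the later record.

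| Discharge day | Day 30 visit held on | Distances | Score kept as Day 30 |
|---|---|---|---|
| 24 | 30 | 6 and 0 | Visit; discharge score discarded |
| 45 | 31 | 15 and 1 | Visit; discharge score discarded |
| 28 | 35 | 2 and 5 | Discharge; scheduled score discarded |
| 28 | 32 | 2 and 2 | Visit (later); discharge score discarded |

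The protocol allows the Day 30 visit 7 days either way, so Days 23 to 37. A discharge after Day 37 is at least 8 days from target and always loses to a Day 30 visit held on time. A discharge on Days 23 to 37 can win or lose. If there is no Day 30 assessment, the discharge score becomes the Day 30 score. The same logic applies in the Day 90 and Day 180 windows.

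**Step 3: what else enters the discharge row.** An ET score, a comfort-care score or an unscheduled score on Days 1 to 22 maps to discharge. The one closest to Day 7 is kept. For example, an unscheduled score on Day 8 (distance 1) beats a true discharge score on Day 20 (distance 13). Even an early discharge score can therefore be displaced.

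**Step 4: how many participants.** The documents give no length-of-stay distribution. With the share discharged on or after Day 23 taken as an assumption, the count is share × N:

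| Assumed share | Of 160 | Of 90 (interim) |
|---|---|---|
| 5% | 8 | 4.5 |
| 10% | 16 | 9 |
| 20% | 32 | 18 |
| 30% | 48 | 27 |

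Efficacy summaries use the mITT set, which may be smaller than 160 or 90, so the counts would be at most these for a given share.

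**Step 5: what depends on the row.** The by-visit GOS-E summary, the interim discharge output and the interim table by GOS-E and visit depend on it directly. The imputation covariate depends on it where a relabelled or misplaced score serves as the previous timepoint. The primary endpoint uses imaging and has no link to it. Observed Day 180 GOS-E changes only where a discharge falls on Day 135 or later and its score is closer to Day 180 than the scheduled one, or where there is no scheduled one.

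**The case against.** The strongest reply is that nothing inferential rests on this row. The GOS-E endpoint is Day 180, with its own window. The same participants are scored again at Days 30, 90 and 180, and those scores are listed beside discharge at the interim. The interim is described as administrative, and both actions that protocol section 16.7 allows continue the blinded study; the only difference is whether Phase 3 preparation is accelerated. All of this stands and limits the importance of the point.

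A second reply is that a fixed early window is a reasonable choice, because scores taken at discharge mix very different times since injury (Day 5 with Day 70, say), and those times may differ by group. As a general point this is fair. It does not rescue the table: SAP sections 4.1 and 5.6.3 both name the timepoint as discharge, and no GOS-E is scheduled at the Day 7 target.

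A third reply is that assigning by label alone creates new problems. A labelled discharge score could be used twice or still displace a Day 30 visit, and it could be later than the Day 30 score, which breaks the time order in the imputation model. This is correct, and the fix has to deal with it.

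A reader might also infer that the discharge summary describes early discharges only and is therefore too favourable. The documents do not support that. The window also admits ET and comfort-care scores. SAP section 5.1.4 scores death as 1 and expects no GOS-E to be missing because of death, so early deaths may be counted there too. Whether the excluded survivors score lower on average than this mixed group cannot be determined. One could assume that 10% to 25% are lost and that their mean is 2 points lower, giving a shift of 0.10 × 2 = 0.2 to 0.25 × 2 = 0.5 points. Both inputs are unsourced, and the result is a shift in an overall mean, not in the treatment difference.

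**Conclusion.** The point holds, as a minor one. Following the SAP as written, a discharge score from Day 23 onward cannot appear in the discharge summary. It is mapped to Day 30, Day 90 or Day 180 according to its date, and non-discharge scores from Days 1 to 22 can be reported as discharge. This follows from the text and needs no assumption.

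The reach is limited to descriptive GOS-E by visit, the interim outputs that use it, and possibly the imputation covariate. No power, sample size or significance level changes.

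The number of participants affected and the direction of any bias cannot be determined from the documents; the 5% to 30% range is illustrative only. A difference in selection between groups would arise if treatment changes length of stay, and the documents do not show whether it does. A reader might also infer that the interim decision on Phase 3 preparation would be distorted. That goes too far: discharge GOS-E is one of many interim outputs, and no decision rule is tied to it.

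**What to change.** Four changes to the SAP:

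1. In Table 1, assign hospital discharge from the CRF visit label, whatever its date.
2. In section 3.1, state that a labelled discharge record may enter the Day 30, Day 90 or Day 180 window only when no other assessment falls in that window.
3. In section 5.1.4, define the previous-timepoint score by date order, so that a discharge after the Day 30 visit is not treated as preceding it.
4. Report time to discharge by treatment group beside the discharge summary, so that a reader can see whether the groups were scored at different times.

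The cost is a few lines of text and one descriptive table. No new data are needed, provided the CRF carries the visit label, as the schedule of activities implies. The downside is small: discharge scores will span a wider range of times since injury, which the fourth change makes visible.

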**Table 2. Study periods, analysis visits and corresponding analysis visit windows.**

Table 2: Study Period	Study Visit	Visit Number	Target Time	Visit Window
Pre-treatment	Pre-Treatment	1	0 h	< 0 h
On-treatment	Hour 0-12	2	12 h	0 - 12 h
	Hour 24	3	24 h	12 - 36 h
	Hour 48	4	48 h	36 - 60 h
	Hour 72	5	72 h	60 - 84 h
	Hour 96	6	96 h	84 - 120 h
	Hour 96 Ext	7	120 h	120 h - 72 h*
Follow-up	Day 30	8	30 d	> 72 h* - 60 d
	Day 90	9	90 d	60 - 150 d
	Day 180	10	180 d	150 - 210 d
	Day 180 Ext	11	270 d	> 210 d

h = hours, d = days. d\* = days from the end of study drug infusion. The Hour 96 Ext visit window of each participant will end 72 hours after the end of study drug infusion, possibly including Day 7 or Discharge operation visits as defined in Table 2 of the protocol. The analysis visit window of Day 30 starts > 72 hours after the end of study drug infusion.

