7. STUDY DESIGN

7.1. Study Overview

This is a Phase 2, randomized, multicenter, double-blind, multidose, placebo-controlled study to assess the efficacy and safety of BIIB093 in inhibiting the progression of traumatic intracerebral contusions in participants aged 18 to 85 years.

Approximately 60 sites in 7 countries globally are planned. The study will randomize 160 participants.

Participants must be treated with BIIB093 within 10 hours of time of trauma/LKN and within 6 hours of hospital arrival. Dosing should be initiated within 1 hour of randomization and continue for 96 hours (4 days). For participants in the 3 mg/day dose arm, treatment will be initiated similarly to the regimen in an ongoing Phase 3 study targeting edema associated with LHI. Participants will receive a bolus IV dose of 0.13 mg (given over approximately 2 minutes), followed by 2 different infusion rates (a rapid IV infusion of 0.1644 mg/h for 6 hours followed by a slow IV infusion of 0.1134 mg/h for the remaining 90 hours). In the 5 mg/day dose arm, participants will receive a bolus IV dose of 0.21 mg (given over approximately 2 minutes), followed by 2 different infusion rates (a rapid IV infusion of 0.2722 mg/h for 6 hours followed by a slow IV infusion of 0.1871 mg/h for the remaining 90 hours). These treatment rates should be administered within the limitation of the device at the site. The treatment duration will be for 96 hours for both treatment groups.

The primary endpoint of this study will be the change in total contusion volume (hematoma plus perihematomal edema) as measured by brain imaging from baseline to 96 hours, or prior to DC, IPH evacuation, or CMO, if these procedures occur before 96 hours.

[figure not shown]
Participants will also have the functional assessments (i.e., GOS-E, [REDACTED], and mRS) performed at both Day 90 and Day 180 post trauma.

After the last participant completes their Day 4 (Hour 96) Visit, data for the primary endpoint and available data for the secondary endpoints will be locked for analysis. The final database lock will occur after the last participant completes their Day 180 Follow-up Visit, marking the end of the study.

See Figure 1 for a schematic of the study design.

CONFIDENTIAL

The information contained herein may not be used, disclosed, or published without the written consent of Biogen MA Inc.

Figure 1: Study Design

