### **3.2. Study Treatment**

All participants must be dosed within 10 hours of time of trauma/last known normal (LKN) and within 6 hours of hospital arrival. Dosing should be initiated within 1 hour of randomization and continue for 96 hours (4 days). Participants will receive study treatment (3 mg/day or 5 mg/day) or matching placebo administered as a 3-stage continuous infusion: a bolus IV dose (given over 2 minutes), followed by 2 different infusion rates (a rapid IV infusion for 6 hours followed by a slow IV infusion for the remaining 90 hours) for 96 hours total. Participants will be randomly assigned to 3 mg/day study treatment, 5 mg/day study treatment, 3 mg/day matching placebo, or 5 mg/day matching placebo in a 1:1:1:1 ratio, stratified based on baseline contusion volume per Investigator assessment of noncontrast computed tomography scan or site local radiologic assessment (3 to 10 mL or > 10 mL), baseline GCS (5 to 8, 9 to 12, or 13 to 15), age ( $\leq$  70 years old or > 70 years old), and region (North America [United States] or Rest of World).

By-treatment-group analysis will be displayed as:

- Placebo
- BIIB093 3 mg/day

- BIIB093 5 mg/day
- BIIB093 combined
- Total, if applicable

The treatment groups are defined as follows.

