## 5.7. Safety [REDACTED]

Adverse events (AEs) will be collected throughout the study and coded using the Medical Dictionary for Regulatory Activities (MedDRA). Adverse events will be summarized based on the principle of treatment emergence.

A treatment-emergent adverse event is defined as 1) any adverse event that has onset on or after start of study drug infusion, or 2) any pre-existing condition that has worsened after start of study drug infusion. On-treatment events are treatment-emergent events that occurred within 3 days after end of study drug infusion. Similarly, on-treatment laboratory data are those from the samples taken from start of study drug infusion to 3 days after the end of study drug infusion. Handling of missing or partial date/time for adverse events and laboratory data is described in Section [5.1](#).

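### SAP Table 2 counts some safety visit windows from Hour 0 and others from infusion end, so for infusions ending before Hour 48 the windows invert and overlap and Day 7 liver tests are labelled Day 30

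*SAP*

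**What the plan says.** SAP 3.1 gives efficacy endpoints their own windows in Table 1 and then turns to Table 2 for everything else ("Study visits and associated visit windows for all remaining analyses are specified in" that second table). In Table 2 the rows from Hour 0-12 to Hour 96 are fixed intervals from Hour 0; the Hour 96 row is 84 to 120 h and sits in the on-treatment period. The next two rows float. Hour 96 Ext starts at 120 h and closes on each participant's own clock, since "The Hour 96 Ext visit window of each participant will end 72 hours after the end of study drug infusion". The footnote then hedges on which scheduled visits this row will catch, "possibly including Day 7 or Discharge operation visits as defined in Table 2 of the protocol". Day 30 follows: "The analysis visit window of Day 30 starts > 72 hours after the end of study drug infusion". There is no row for Day 7 or for discharge.

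In the schedule of activities (Protocol section 5, Table 2), the row "Blood sampling for LFTs" is marked at Screening, Hours 24, 48, 72 and 96, and Day 7 (± 24 h), and not at Day 30. SAP 5.7.4 also names Day 7 as a glucose collection time.

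SAP 3.3 ends the on-treatment period, and starts follow-up, 72 hours after the end of infusion. SAP 5.7 uses the same limit: "On-treatment events are treatment-emergent events that occurred within 3 days after end of study drug infusion". The by-visit part of SAP 5.7.4 plans actual values, change, percent change and mean plots for each laboratory parameter.

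**The concern.** A visit window should place each sample in exactly one visit, and the label should tell the reader when the sample was taken. Mixing two anchors breaks both properties for participants whose infusion ends early. Protocol 10.1 asks those participants to stay in the study and continue their assessments, so their Hour 96 and Day 7 samples will exist.

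At stake is the readability of the by-visit laboratory tables. A Day 30 liver row would consist mainly of Day 7, discharge or unscheduled samples, at a time point where no liver test is planned. One scheduled visit could be split over two rows. For early stoppers, a programmer would have to choose between two rows with no stated rule.

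**Working it through.** **Inputs.** Let E be the hours from Hour 0 to the end of a participant's infusion. The planned length is 96 h (SAP 3.2), and Protocol 11.2 does not extend it after stoppages, so E is about 96 at most. Table 2 marks the floating limits with an asterisk on hours while its key defines the asterisk on days; I read both as time from infusion end, as the footnote's sentences say.

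**Windows as written.**
- Hour 96: 84 to 120 h
- Hour 96 Ext: 120 h to E + 72, so its length is E + 72 − 120 = E − 48
- Day 30: after E + 72, up to 60 days

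**Two readings of Day 7 (± 24 h).**
- *Study Day 7.* SAP 3.1 makes the infusion-start date Day 1, so Day 7 falls six days later, at about 6 × 24 = 144 h. The visit window is then 120 to 168 h.
- *Elapsed Day 7.* Protocol 7.1 pairs Day 4 with Hour 96 ("After the last participant completes their Day 4 (Hour 96) Visit"). Since 4 × 24 = 96, the same count gives 7 × 24 = 168 h, and a visit window of 144 to 192 h.

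**Results.** The shares below are shares of window time. They equal shares of samples only if samples are spread evenly.

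| E (h) | E + 72 (h) | Length of Hour 96 Ext (h) | Share of 84-120 h also in Day 30 | Share of Day 7 visit in Day 30, 120-168 h | Share of Day 7 visit in Day 30, 144-192 h |
|---|---|---|---|---|---|
| 12 | 84 | −36 | 100% | 100% | 100% |
| 24 | 96 | −24 | 67% | 100% | 100% |
| 36 | 108 | −12 | 33% | 100% | 100% |
| 48 | 120 | 0 | 0% | 100% | 100% |
| 72 | 144 | 24 | 0% | 50% | 100% |
| 96 | 168 | 48 | 0% | 0% | 50% |

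For example, at E = 24 the overlap is (120 − 96)/36 = 67%. At E = 96 under the elapsed reading, the share is (192 − 168)/48 = 50%.

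**Thresholds.**
- Overlap with the Hour 96 row needs E + 72 < 120, so E < 48.
- Within the protocol's own Hour 96 tolerance (± 12 h, so 84 to 108 h), overlap needs E < 36.
- A sample at exactly 96 h fits both rows only if E < 24.
- The whole Hour 96 row is covered if E + 72 ≤ 84, so E ≤ 12.

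**Is there a tie-break?** The closest-to-target rule in SAP 3.1 is introduced for efficacy data and chooses between records in one window. The worst-record rule for ECGs in SAP 5.7.5 also works within one window. Neither chooses between two windows.

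**Period conflict.** For E < 48, Table 2 lists all of 84 to 120 h as on-treatment, while SAP 3.3 puts the part after E + 72 in follow-up.

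**Reach.** SAP 5.7.4 summarizes laboratory data by visit and so uses these labels. The by-visit ECG summary in SAP 5.7.5 uses them too, but the last scheduled trace is at Hour 96, so only participants stopped before about Hour 24 are touched. Outputs that do not depend on the labels are shift tables, potentially clinically significant abnormalities, lowest glucose, maximum liver values, study-long adverse event tables and the primary endpoint, which has its own windows in Table 1.

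**The case against.** The strongest reply is that the design works for most participants. Under the SAP's own day count, a completer's Day 7 visit (120 to 168 h) coincides exactly with Hour 96 Ext, as the Table 2 footnote foresees. Protocol Table 1 also counts dosing days as 24-hour periods, which puts Day 7 at Hours 144 to 168. Discharge before Day 7 pulls those assessments earlier still. This stands: completers are largely unaffected, and the 50% figure is the upper case.

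A second reply is that Table 2 nests visits within periods. Read period first, a sample more than 72 hours after infusion end is follow-up and cannot be Hour 96. That reading removes the double fit, but the SAP does not state it. It would also relabel the scheduled Hour 96 sample of an early stopper as Day 30.

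Third, infusion end plus 72 hours is justified in SAP 3.3 by half-life and drug clearance. That stands for the on-treatment definition. An on-treatment period that closes early after an early stop is that definition at work. It does not justify using the same limit to name a visit.

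A reader might also infer that the mislabelling biases the comparison between arms, because hypoglycemia or the liver stopping rule would end more BIIB093 infusions early. The documents do not support that. They give no rate of stopping before Hour 48. Hypoglycemia leads first to a rate reduction (Protocol 11.2), which does not move the infusion end. Protocol 4.3.3 identifies hypoglycemia as the only adverse drug reaction, so an excess of liver stops has no stated basis. Nor does SAP 5.7.6 plan by-visit vital-sign tables, so extending the point to vital signs goes beyond the text.

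**Conclusion.** The defect is real and minor. As written, Table 2 yields an inverted Hour 96 Ext window and an overlap between Hour 96 and Day 30 whenever the infusion ends before Hour 48. It also labels as Day 30 every liver test that such a participant has within the Day 7 visit window, under either reading of Day 7. Stops between Hour 48 and Hour 96 cause no overlap, but part or all of the Day 7 window is mislabelled. For completers, only samples after Hour 168 are mislabelled.

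The number affected is unknown because no early-stop rate is given. The SAP does foresee very early stops: its per-protocol set (3.6.2) excludes infusions discontinued within 12 hours, the group in which Day 30 covers nearly all or all of the Hour 96 row. The conclusion rests on taking E as the actual end of a participant's infusion and on early stoppers being sampled on schedule. It does not bear on the primary endpoint, or on safety outputs based on any post-baseline value.

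**What to change.** Before the Day 4 administrative lock, revise SAP Table 2 as follows:
- Define every visit window from Hour 0.
- Add a Day 7 and discharge row that starts after 120 h.
- Start Day 30 where that row ends, for example at day 23, as Table 1 already does for GOS-E. Later discharge samples then stay out of Day 30 as well.
- State which record is used when several safety samples fall in one window, since the existing closest-to-target rule is written for efficacy data.
- Keep infusion end plus 72 hours as a separate on-treatment flag, independent of the visit label, and remove the fixed period heading from rows where the two can disagree.

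A fixed Hour 0 to 168 summary of adverse events and laboratory data would be optional and is not part of this correction.

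The cost is a table edit and some reprogramming of safety outputs. Data collection, treatment, sample size and the primary analysis do not change. SAP 3.1 states that Table 2 may still change before that lock.
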